7.1 Dose reductions and modifications

There will be no dose reduction or modifications in Immunotherapy administration.

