4.3 Immunotherapy

Immunotherapy will be delivered in the form of PD-1/PD-L1 blockade using approved anti PD-1/PD-L1 agents. Dose reductions are appropriate for toxicity as specified or at the discretion of the treating medical oncologist. Prior immunotherapy as part of multi-drug therapy or monotherapy is acceptable prior to initiation of SBRT.

The DLT observation period for continuation or discontinuation of therapy is defined as 14 days starting with cycle 1, day 1. To be evaluable for DLT, a patient must have received at least the first 2 administrations and be monitored for at least 14 days following the first administration. Any of the below outlined events occurring during each DLT observation period and considered to be at least possibly related to Nivolumab will qualify as a DLT.

Non-Hematologic Toxicity

1. Grade ≥ 2 uveitis
2. Any Grade ≥ 3 non-hematologic toxicity except
 - a. Nausea, vomiting or diarrhea
 - b. Clinically insignificant laboratory abnormalities
 - c. Grade 3 infusion reactions that respond to medical management
 - d. Grade 3 immune related effects other than uveitis that improve within 7-14 days with steroid treatment (Appendix 1).

Hematologic Toxicity

1. Grade 4 neutropenia lasting more than 1 week
2. Grade 4 thrombocytopenia
3. Grade 3 thrombocytopenia with bleeding
4. Grade ≥ 3 febrile neutropenia

Special

1. Grade ≥ 2 pneumonitis

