7. IMMUNOTHERAPY

Immunotherapy administration will commence or continue following the conclusion of SBRT/SABR.

Immunotherapy will be administered as an IV infusion as specified. It is not to be administered as an IV push or bolus injection. At the end of the infusion the administration line will be flushed with a sufficient quantity of normal saline per standard of care. Infusions will continue on a standard schedule for the specific immunotherapy agent with pre-treatment assessments for adverse effects using a standard questionnaire.

Immunotherapy administration will be delayed in the case of any of the following:

Any Grade ≥ 2 non-skin, drug-related adverse event, with the following exceptions:— Grade 2 drug-related fatigue or laboratory abnormalities do not require a treatment delay

Any Grade 3 skin, drug-related adverse event

Any Grade 3 drug-related laboratory abnormality, with the following exceptions for lymphopenia, leukopenia, AST, ALT, or total bilirubin:

- Grade 3 lymphopenia or leukopenia does not require dose delay
- If a subject has a baseline AST, ALT or total bilirubin that is within normal limits, delay dosing for drug-related Grade ≥ 2 toxicity
- If a subject has baseline AST, ALT, or total bilirubin within the Grade 1 toxicity range, delay dosing for drug-related Grade ≥ 3 toxicity

Any adverse event, laboratory abnormality, or intercurrent illness which, in the judgment of the investigator, warrants delaying immunotherapy administration.

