
• Enterocolitis hemorrhagic
 
 • Gastrointestinal (GI) perforation • Necrotizing colitis 
Diarrhea: Patients who experience diarrhea should be advised to drink liberal quantities of clear fluids. If sufficient oral fluid intake is not feasible, fluid and electrolytes should be substituted via IV infusion.
	
Grade 2
	
Hold until ≤Grade 1. Resume at same dose level. May increase dosing interval by 1 week if it takes more than 4 weeks for toxicities to resolve.
	
GI consultation and endoscopy is recommended to confirm or rule out colitis for grade 2 diarrhea that persists >1 week or grade 1-2 diarrhea with rectal bleeding (additional guidelines for the treatment of persistent colitis are provided below). Grade 2 diarrhea should be treated with the addition of oral diphenoxylate hydrochloride and atropine sulfate four times daily and budesonide 9 mg daily. Grade 2 diarrhea with diffuse ulceration and bleeding seen on endoscopy may require oral steroids with prolonged taper and represent an increased risk for the development of bowel perforation. Consider prophylactic antibiotics for opportunistic infections. When symptoms improve to Grade 1 or less, steroid taper should be started and continued over no less than 4 weeks. • In patients with Grade 2 enterocolitis, IMMUNOTHERAPY should be withheld and anti-diarrheal treatment should be started. If symptoms are persistent for more than one week, systemic corticosteroids should be initiated (eg, 0.5 mg/kg/day of prednisone or equivalent). When symptoms improve to Grade 1 or less, corticosteroid taper should be started and continued over at least 1 month.
	
 • Blood and/or mucus in stool with or without fever • Constipation • Diarrhea • Ileus • Nausea and/or vomiting • Peritoneal signs consistent with bowel perforation • Rectal bleeding • With or without fever 
Patients with diarrhea should be
	
or parasitic infection, viral gastroenteritis, or the first manifestation of an inflammatory bowel disease by examination for stool leukocytes, stool cultures, and a Clostridium difficile titer.

Event(s)	CTCAE v4.03 Grade	Management	Action/Supportive Care Guidelines

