Eye event: Uveitis (iritis, iridocyclitis)	Grade 1	Discontinue IMMUNOTHERAPY if symptoms persist despite treatment with topical immunosuppressive therapy	
 • Evaluation by an ophthalmologist is strongly recommended. • Treat with topical steroids such as 1% prednisolone acetate suspension and iridocyclitics. 	Symptoms may include (but are not limited to): 
 • Blurred vision • Diffuse erythema and a prominent blush on the sclerae • Dryness of the eyes • Pain • Photophobia 	All attempts should be made to rule out other causes such as metastatic disease, infection, or other ocular disease (e.g., glaucoma or cataracts).
	Grade 2	Discontinue IMMUNOTHERAPY if symptoms persist despite treatment with topical immunosuppressive therapy and do not improve to Grade 1 within the retreatment period OR requires systemic treatment.	
 • Evaluation by an ophthalmologist is strongly recommended. • Treat with topical steroids such as 1% prednisolone acetate suspension and iridocyclitics. 		
	Grade 3-4	Discontinue IMMUNOTHERAPY.	
 • Treat with systemic corticosteroids such as prednisone at a dose of 1-2 mg/kg per day. When symptoms improve to \leq Grade 1, steroid taper should be started and continued over no less than 4 weeks. 		

Event(s)	CTCAE v4.03 Grade	Management	Action/Supportive Care Guidelines	Symptoms ^a	Differential Diagnosis
Hepatic events 
 Hepatitis Hepatitis, Autoimmune 	Grade 1-2	Withhold IMMUNOTHERAPY if there is a treatment-emergent concurrent elevation of ALT and bilirubin that corresponds to an upward shift of 2 or more grades in both parameters.	
 Monitor liver function tests more frequently until returned to baseline values. 	Symptoms may include (but are not limited to): 
 Elevations in: 
 AST >2.5 ULN ALT >2.5 ULN Total bilirubin >1.5 × ULN 	All attempts should be made to rule out other causes such as metastatic disease, progressive liver disease, viral hepatitis,

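### Sections 4.3 and 7.1 contradict each other on immunotherapy dose reduction, and section 7 orders delays for some events where Appendix I would continue dosing, with no stated precedence

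*Protocol*

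**What the plan says.** **Dose level.** Protocol section 4.3 (Immunotherapy): "Dose reductions are appropriate for toxicity as specified or at the discretion of the treating medical oncologist". Section 7.1: "There will be no dose reduction or modifications in Immunotherapy administration".

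**Delay.** Section 7 opens its list of triggers with "Immunotherapy administration will be delayed in the case of any of the following". The triggers include any drug-related non-skin event of Grade 2 or higher, except Grade 2 fatigue and Grade 2 laboratory abnormalities. They also include "Any Grade 3 drug-related laboratory abnormality, with the following exceptions for lymphopenia, leukopenia, AST, ALT, or total bilirubin". Under that second trigger, for patients with "baseline AST, ALT or total bilirubin that is within normal limits, delay dosing for drug-related Grade ≥ 2 toxicity".

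**Appendix I.** This is a separate table of recommended actions by event and grade. For Grade 1-2 hepatic events it withholds treatment only for a "concurrent elevation of ALT and bilirubin that corresponds to an upward shift of 2 or more grades in both parameters". It lets dosing continue unchanged for Grade 1-2 thyroid events, for Grade 3 neutropenia, and for Grade 3 thrombocytopenia unless that lasts more than 7 days or is accompanied by bleeding. It permits a longer dosing interval, for example after Grade 2 colitis: "Resume at same dose level. May increase dosing interval by 1 week if it takes more than 4 weeks for toxicities to resolve".

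**Link between the two.** Section 7 does not mention Appendix I. The only reference to it in the body text is in the section 4.3 list of exceptions to dose-limiting toxicity, at the item beginning "Grade 3 immune related effects other than uveitis that improve within 7-14 days with steroid treatment (Appendix 1".

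**The concern.** A treating oncologist who meets a toxicity needs one instruction. Under 4.3 the dose may be lowered at discretion and without limit; under 7.1 it may not be lowered at all. For some events section 7 requires a delay while Appendix I tells the same oncologist to carry on. Two clinicians could each follow the protocol and treat the same event in opposite ways.

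This matters for two reasons that the protocol itself gives. Safety, feasibility and tolerability are the primary objective of the pilot phase (section 3.1). Section 2.1 relies on FDA-approved dosing so that outcomes can be compared with trials of immunotherapy alone, and section 4.1 promises standard dosing. Discretionary reductions would undercut that.

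**Working it through.** No arithmetic beyond grade counting applies. The check sets the texts side by side.

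**1. Section 4.3 against 7.1.** Both are current body text and both concern immunotherapy. One allows reduction and the other forbids it. Section 4.3 points to reductions that are specified, but no dose levels are given in section 7 or in Appendix I. The Appendix I renal entry, which lets the dose be modified as the protocol specifies, therefore points to nothing.

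**2. Section 7 against Appendix I.**

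| Event (drug-related) | Section 7 | Appendix I | Standing |
|---|---|---|---|
| Isolated Grade 2 AST, ALT or bilirubin rise, normal baseline | Delay (specific hepatic bullet) | Not withheld | Conflict |
| Grade 3 thrombocytopenia | Delay (Grade 3 laboratory event, not excepted) | Dosing unchanged unless over 7 days or bleeding | Conflict; row identified from its guideline text |
| Clinical Grade 2 thyroid event | Delay (non-skin, Grade 2 or higher) | Dosing unchanged | Conflict, if not laboratory-only |
| Grade 3 neutropenia | Delay, unless leukopenia is meant to cover it | Dosing unchanged | Conditional |
| Clinical Grade 2 renal event | Delay, if not laboratory-only | Withholding optional | Conditional |
| Grade 2 pneumonitis; Grade 3 skin | Delay | Hold | Agree |

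*Hepatic row, step by step.* A normal baseline is Grade 0. If only ALT rises to Grade 2, the shift is 2 - 0 = 2 grades in ALT and 0 in bilirubin. Section 7's hepatic bullet is met (Grade 2 or higher), so dosing is delayed. Appendix I needs a shift of 2 or more in both ALT and bilirubin; only one qualifies, so dosing continues. If both reach Grade 2, the texts agree. Appendix I's condition does not name AST, so an AST rise alone never meets it.

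Section 7 is also unclear within itself here. Its first trigger exempts Grade 2 laboratory abnormalities, and the hepatic bullet then orders delay at Grade 2. The specific rule probably governs, but this is not stated.

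*Meaning of unchanged dosing.* It cannot be read as delaying and then resuming at the same dose, because other cells in the same Appendix I column order a hold when a pause is intended.

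**3. Within Appendix I.** For Grade 3-4 colitis the management cell withholds treatment and discontinues only if steroids cannot be tapered within 12 weeks. The guideline cell permanently discontinues nivolumab for Grade 3 enterocolitis. Hypophysitis also seems to appear in two rows with different actions, and the Grade 3-4 renal row seems both to discontinue and to allow restart. The available text of those tables is broken, so these two need checking against the original layout.

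**The case against.** The best defence is that section 7 is mandatory, Appendix I is only recommended, and section 7's last item lets the investigator delay for any event. A clinician who delays therefore never breaches section 7. That reading is sensible, but no sentence states it. It also leaves 4.3 against 7.1 and the enterocolitis entry untouched.

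The Appendix I hepatic row is headed for hepatitis, so applying it to an isolated enzyme rise is an inference. Its symptom cell, however, lists AST, ALT and bilirubin elevations. The enterocolitis sentence could be a specific rule inside a general row, since the row also covers diarrhea. That is possible, but it still gives Grade 3 enterocolitis on nivolumab two actions.

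Four stronger readings are tempting, and the protocol does not support them:

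- *The hepatic conflict reaches essentially every patient, because inclusion criterion 7 requires normal hepatic function.* Normal has no numeric limit there, section 7 itself provides for Grade 1 baselines, and Appendix III schedules follow-up liver tests only when SBRT was delivered to the liver. Other cases would have to surface in routine care.
- *Section 7.1 bars the longer intervals in Appendix I.* Its parent section orders delays, so modifications cannot sensibly include timing.
- *Section 7 should simply prevail.* Its delay trigger covers every non-skin event of Grade 2 or higher. Blanket precedence would turn Appendix I's discontinuations for Grade 3-4 pneumonitis, uveitis, hepatic and renal events into mere delays.
- *The statistical design is compromised.* No endpoint, sample size, error rate or pneumonitis rule depends on these sentences.

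**Conclusion.** The point holds as a defect in the current text that should be corrected. There is one direct contradiction on dose reduction (4.3 against 7.1). There are three examples where section 7 delays and Appendix I continues, two further conditional examples, and one event in Appendix I with two actions.

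The dose-reduction and hepatic conflicts are the firmest, since they do not depend on uncertain table rows. The hepatic one assumes that the specific bullet overrides the general Grade 2 laboratory exemption. The thrombocytopenia example rests on guideline text that names the event and grade within a broken table. The thyroid example assumes a clinical event rather than a laboratory finding alone.

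How many of the planned 100 patients (20 in the pilot) would meet these events cannot be derived from the protocol. The consequence is inconsistent safety instructions and possibly non-uniform dosing; it is not a change in any statistical operating characteristic.

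**What to change.** (a) Delete the dose-reduction sentence from 4.3. Restate 7.1 as: no dose reductions; delay, interval extension and discontinuation are allowed as listed in section 7 and Appendix I. Remove the clause about a modified dose from the Appendix I renal entry.

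(b) Add to section 7: where section 7 and Appendix I differ, the more cautious action applies; section 7's delay applies where Appendix I would continue dosing, and Appendix I's discontinuation rules stand. Align the Grade 3 thrombocytopenia, Grade 1-2 hepatic and Grade 2 endocrine rows with this. State that the hepatic bullet overrides the Grade 2 laboratory exemption, and whether leukopenia includes neutropenia.

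(c) Give Grade 3 enterocolitis one action, with the investigators confirming the clinical choice. Check the hypophysitis and renal rows against the original table.

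The cost is a wording amendment, with no new data and no additional patients.

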7.2 Treatment Compliance

Treatment compliance will be monitored by the site P.I and documented in the medical record.

8.0 PATIENT ASSESSMENTS

8.1 Study Parameters

See Appendix III

8.2 Data Collection

Patients will be stratified by number of metastatic lesions. ≤ 3 lesions, 4-5 lesions and ≥ 5 lesions.

All study data will be coded and de-identified. Codes and patient data will be stored separately in a password protected file. Any hard copies will be stored in a locked file cabinet. All other data will be stored on a password secured and encrypted computer only accessible to study staff.

Adverse event data collection and reporting, which are required as part of every clinical trial, are done to ensure the safety of patients enrolled in the studies as well as those who will enroll in future studies using similar agents. Adverse events are reported in a routine manner at scheduled times during the trial by the study investigator.

For pre-specified time points and required reporting please see Appendix IV.

APPENDIX I. RECOMMENDED DOSE MODIFICATION OR DISCONTINUATION AND SUPPORTIVE CARE GUIDELINES FOR SPECIFIC DRUG-RELATED ADVERSE EVENTS

Event(s)	CTCAE v4.03 Grade	Management	Action/Supportive Care Guidelines	Symptoms ^a	Differential Diagnosis

Colitis events
 
 • Bowel obstruction • Colitis • Colitis microscopic 	
≤ Grade 1
	
No change in dose
	
For diarrhea, treat symptomatically (loperamide, oral hydration, electrolyte substitution and ADA colitis diet). Endoscopy is recommended if symptoms persist.
 
 • Grade 1 diarrhea that persist for >1 week should be treated with the addition of oral diphenoxylate hydrochloride and atropine sulfate four times daily and budesonide 9 mg daily. 	
Symptoms may include (but are not limited to):
 
 • Abdominal pain, cramping and/or bloating 	
All attempts should be made to rule out other causes such as metastatic disease, bacterial or parasitic infection, viral gastroenteritis, or the first manifestation of an inflammatory bowel disease by examination for stool leukocytes, stool cultures, and a Clostridium difficile titer.


• Enterocolitis hemorrhagic
 
 • Gastrointestinal (GI) perforation • Necrotizing colitis 
Diarrhea: Patients who experience diarrhea should be advised to drink liberal quantities of clear fluids. If sufficient oral fluid intake is not feasible, fluid and electrolytes should be substituted via IV infusion.
	
Grade 2
	
Hold until ≤Grade 1. Resume at same dose level. May increase dosing interval by 1 week if it takes more than 4 weeks for toxicities to resolve.
	
GI consultation and endoscopy is recommended to confirm or rule out colitis for grade 2 diarrhea that persists >1 week or grade 1-2 diarrhea with rectal bleeding (additional guidelines for the treatment of persistent colitis are provided below). Grade 2 diarrhea should be treated with the addition of oral diphenoxylate hydrochloride and atropine sulfate four times daily and budesonide 9 mg daily. Grade 2 diarrhea with diffuse ulceration and bleeding seen on endoscopy may require oral steroids with prolonged taper and represent an increased risk for the development of bowel perforation. Consider prophylactic antibiotics for opportunistic infections. When symptoms improve to Grade 1 or less, steroid taper should be started and continued over no less than 4 weeks. • In patients with Grade 2 enterocolitis, IMMUNOTHERAPY should be withheld and anti-diarrheal treatment should be started. If symptoms are persistent for more than one week, systemic corticosteroids should be initiated (eg, 0.5 mg/kg/day of prednisone or equivalent). When symptoms improve to Grade 1 or less, corticosteroid taper should be started and continued over at least 1 month.
	
 • Blood and/or mucus in stool with or without fever • Constipation • Diarrhea • Ileus • Nausea and/or vomiting • Peritoneal signs consistent with bowel perforation • Rectal bleeding • With or without fever 
Patients with diarrhea should be
	
or parasitic infection, viral gastroenteritis, or the first manifestation of an inflammatory bowel disease by examination for stool leukocytes, stool cultures, and a Clostridium difficile titer.

Event(s)	CTCAE v4.03 Grade	Management	Action/Supportive Care Guidelines
Colitis events (continued)	Grade 3–4	
Withhold IMMUNOTHERAPY
 
Discontinue if unable to reduce corticosteroid dose to < 10 mg per day prednisone equivalent within 12 weeks of toxicity
	
 • In patients with Grade 3 enterocolitis, OPDIVO will be permanently discontinued and treatment with systemic corticosteroids should be initiated at a dose of 1–2 mg/kg/day of prednisone or equivalent. When symptoms improve to Grade 1 or less, corticosteroid taper should be started and continued over at least 1 month. Consider prophylactic antibiotics for opportunistic infections. 
For Grade 3–4 diarrhea (or Grade 2 diarrhea that persists after initial steroid treatment),
 
 • Rule out bowel perforation. Imaging with plain films or computed tomography (CT) can be useful. • Consider consultation with gastroenterologist and confirmation biopsy with endoscopy. • Treat with intravenous (IV) steroids (methylprednisolone 125 mg) followed by high-dose oral steroids (prednisone 1–2 mg/kg once per day or dexamethasone 4 mg every 4 hours). When symptoms improve to Grade 1 or less, steroid taper should be started and continued over no less than 4 weeks. Taper over 6–8 weeks in patients with diffuse and severe ulceration and/or bleeding. • If IV steroids followed by high-dose oral steroids does not reduce initial symptoms within 48–72 hours, consider treatment with infliximab at 5 mg/kg once every 2 weeks. Discontinue infliximab upon symptom relief and initiate a prolonged steroid taper over 45–60 days. If symptoms worsen during steroid reduction, initiate a tapering of steroids starting at a higher dose of 80 or 100 mg followed by a more prolonged taper and administer infliximab. CAUTION: infliximab is contraindicated in patients with bowel perforation or sepsis^b. • If symptoms persist despite the above treatment a surgical consult should be obtained.

Event(s)	CTCAE v4.03 Grade	Management	Action/Supportive Care Guidelines	Symptoms ^a	Differential Diagnosis
Endocrine events 
 • Hyperthyroidism • Hypophysitis • Hypopituitarism 	Grade 1-2	No change in dose	
 • Monitor thyroid function or other hormonal level tests and serum chemistries more frequently until returned to baseline values. 	Symptoms may include (but not limited to): 
 • Abdominal pain 	All attempts should be made to rule out other causes such as brain metastases,
Endocrine events 
 • Hypothyroidism • Thyroid disorder • Thyroiditis 	Grade 3-4	Hold until on stable replacement dose	
 • Consider endocrine consultation. • Rule out infection and sepsis with appropriate cultures and imaging. • Replacement of appropriate hormones as required. 	
 • Abnormal thyroid function tests and/or serum chemistries (Thyroid-stimulating hormone increased [decreased], Free thyroxine increased, Tri-iodothyronine increased.) 	sepsis, and/or infection. An endocrinology consultation is recommended.
Endocrine events 
 • Adrenal insufficiency • Hypophysitis • Pan-hypopituitarism 	Grade 1-4	Hold until on stable replacement dose	
 • Thyroid hormone and/or steroid replacement therapy to manage adrenal insufficiency. • If Grade 1-2 hypophysitis is considered, pituitary gland imaging should be considered (magnetic resonance imaging [MRIs] with gadolinium and selective cuts of the pituitary can show enlargement or heterogeneity and confirm the diagnosis). • Grade 3-4 hypophysitis with clinically significant adrenal insufficiency and hypotension, dehydration, and electrolyte abnormalities (such as hyponatremia and hyperkalemia) constitutes adrenal crisis. Hospitalization and IV methylprednisolone should be initiated. 	
 • Arrhythmias^c • Cold or heat intolerance • Fatigue • Fever • Headache • Hypotension^c • Loss of appetite • Mental status and/or behavior changes • Nausea and/or vomiting • Unusual bowel habits • Vision disturbances 	

Event(s)	CTCAE v4.03 Grade	Management	Action/Supportive Care Guidelines	Symptoms ^a	Differential Diagnosis
Eye event: Uveitis (iritis, iridocyclitis)	Grade 1	Discontinue IMMUNOTHERAPY if symptoms persist despite treatment with topical immunosuppressive therapy	
 • Evaluation by an ophthalmologist is strongly recommended. • Treat with topical steroids such as 1% prednisolone acetate suspension and iridocyclitics. 	Symptoms may include (but are not limited to): 
 • Blurred vision • Diffuse erythema and a prominent blush on the sclerae • Dryness of the eyes • Pain • Photophobia 	All attempts should be made to rule out other causes such as metastatic disease, infection, or other ocular disease (e.g., glaucoma or cataracts).
	Grade 2	Discontinue IMMUNOTHERAPY if symptoms persist despite treatment with topical immunosuppressive therapy and do not improve to Grade 1 within the retreatment period OR requires systemic treatment.	
 • Evaluation by an ophthalmologist is strongly recommended. • Treat with topical steroids such as 1% prednisolone acetate suspension and iridocyclitics. 		
	Grade 3-4	Discontinue IMMUNOTHERAPY.	
 • Treat with systemic corticosteroids such as prednisone at a dose of 1-2 mg/kg per day. When symptoms improve to \leq Grade 1, steroid taper should be started and continued over no less than 4 weeks. 		

Event(s)	CTCAE v4.03 Grade	Management	Action/Supportive Care Guidelines	Symptoms ^a	Differential Diagnosis
Hepatic events 
 Hepatitis Hepatitis, Autoimmune 	Grade 1-2	Withhold IMMUNOTHERAPY if there is a treatment-emergent concurrent elevation of ALT and bilirubin that corresponds to an upward shift of 2 or more grades in both parameters.	
 Monitor liver function tests more frequently until returned to baseline values. 	Symptoms may include (but are not limited to): 
 Elevations in: 
 AST >2.5 ULN ALT >2.5 ULN Total bilirubin >1.5 × ULN 	All attempts should be made to rule out other causes such as metastatic disease, progressive liver disease, viral hepatitis,
	Grade 3-4	Discontinue IMMUNOTHERAPY when 
 AST or ALT >5.0 times ULN and/or total bilirubin >3.0 times ULN. 	
 Consider appropriate consultation and liver biopsy to establish etiology of hepatic injury, if necessary. Treat with high-dose IV glucocorticosteroids for 24-48 hours. When symptoms improve to grade 1 or less, a steroid taper with dexamethasone 4 mg every 4 hours or prednisone at 1-2 mg/kg should be started and continued over no less than 4 weeks. If serum transaminase levels do not decrease 48 hours after initiation of systemic steroids, oral mycophenolate mofetil 500 mg every 12 hours may be given. Infliximab is not recommended due to its potential for hepatotoxicity^b. Several courses of steroid tapering may be necessary as symptoms may worsen when the steroid dose is decreased. 	
 Fever Malaise Upper quadrant abdominal pain 	alternative drug toxicity, infectious causes and/or myositis.

CTCAE Management

Symptoms^a

Differential

Event(s)	v4.03 Grade	Management	Action/Supportive Care Guidelines	Diagnosis
Neutropenia	≤Grade 1	No change in dose		
	Grade 2	No change in dose		
	Grade 3	No change in dose		
	Grade 4	Hold until resolves to ≤Grade 1. May increase the dosing interval by 1 week. Discontinue if toxicities do not resolve within 12 weeks.		

Event(s)	CTCAE v4.03 Grade	Management	Action/Supportive Care Guidelines	Symptoms ^a	Differential Diagnosis
Pneumonitis events • Interstitial lung disease • Acute interstitial pneumonitis	Grade 1	Consider hold of therapy. IMMUNOTHERAPY may be continued with close monitoring.	
 • Radiologic findings should be followed on serial imaging studies at least every 3 weeks. • Monitor for symptoms every 2-3 days. • Consider pulmonary consultation and/or bronchoscopy if clinically indicated. 	Symptoms may include (but are not limited to): 
 • Abnormal breath sounds • Chest pain and/or tightness^c • Dyspnea^c • Dry cough • Fatigue 	All attempts should be made to rule out other causes such as metastatic disease, bacterial or viral infection.
	Grade 2	Hold IMMUNOTHERAPY	To rule out other causes such as infection: 
 • Consider pulmonary consultation with bronchoscopy and biopsy/bronchoalveolar lavage (BAL). • Consider pulmonary function tests. • Follow radiologic findings on serial imaging studies every 1-3 days If the patient is determined to have study drug associated pneumonitis: 
 • Monitor symptoms daily; consider hospitalization. • Treat with systemic corticosteroids at a dose of 1-2 mg/kg/day prednisone or equivalent. When symptoms improve to Grade 1 or less, steroid taper should be started and continued over no less than 4 weeks. • Treatment with IMMUNOTHERAPY may be resumed if the event improves to ≤ Grade 1 within 12 weeks and corticosteroids have been reduced to the equivalent of methylprednisolone 10 mg by mouth daily or less. Repeat chest imaging monthly as clinically indicated. For Grade 2 pneumonitis that improves to	
 • Fever • Hemoptysis 	

Grade 3-4	Discontinue IMMUNOTHERAPY.	
≤Grade 1 within 12 weeks, the following rules should apply:
 
 • First episode of pneumonitis: May increase dosing interval by one week in subsequent cycles. • Second episode of pneumonitis: Discontinue IMMUNOTHERAPY if upon rechallenge the patient develops a second episode of ≥ Grade 2 pneumonitis. 
 • Consider pulmonary function tests with pulmonary consult. • Bronchoscopy with biopsy and/or BAL is recommended. • Treat with IV steroids (2-4 mg/kg per day prednisone or equivalent). When symptoms improve to grade 1 or less, a high-dose oral steroid (1-2 mg/kg prednisone once per day or 4 mg dexamethasone every 4 hours) taper should be started and continued over no less than 4 weeks. • Add prophylactic antibiotics for opportunistic infections. • If IV steroids followed by high-dose oral steroids does not reduce initial symptoms within 48-72 hours, treat with infliximab at 5 mg/kg once every 2 weeks. Discontinue infliximab upon symptom relief and initiate a prolonged steroid taper over 45-60 days. If symptoms worsen during steroid reduction, initiate a retapering of steroids starting at a higher dose of 80 or 100 mg followed by a more prolonged taper and administer infliximab. 		
-----------	----------------------------	--	--	--

CTCAE	Management/	Symptoms ^a	Differential
-------	-------------	-----------------------	--------------

Event(s)	v4.03 Grade	Action/Supportive Care Guidelines	Symptoms	Diagnosis
Renal events	Grade 1	
 Consider withholding IMMUNOTHERAPY if event does not improve with symptomatic treatment 	
 Provide symptomatic treatment. Monitor creatinine weekly; when it returns to baseline, resume routine creatinine monitoring per protocol. 	
All attempts should be made to rule out other causes such as obstructive uropathy, progression of disease, or injury to other chemotherapy agents. A renal consultation is recommended.

	Grade 2	
 Consider withholding IMMUNOTHERAPY. 	
 Systemic corticosteroids at a dose of 1-2 mg/kg/day of prednisone or equivalent may be indicated. When symptoms improve to Grade 1 or less, corticosteroid taper should be started and continued over at least 1 month. Consider prophylactic antibiotics for opportunistic infections. Consider renal biopsy. If elevations persist >7 days or worsen, treat as Grade 4. 	
Renal failure, Acute	Grade 3-4	
 Discontinue IMMUNOTHERAPY. 	
 Renal consultation with consideration of ultrasound and/or biopsy as appropriate. Monitor creatinine daily. Treat with systemic corticosteroids at a dose of 1-2 mg/kg prednisone or equivalent once per day. When symptoms improve to grade 1 or less, steroid taper should be started and continued over no less than 4 weeks. Discontinue IMMUNOTHERAPY if unable to reduce corticosteroid dose for irAEs to ≤10 mg. IMMUNOTHERAPY treatment may be restarted and the dose modified as specified in the protocol. 	
 Symptoms may include (but not limited to): Fatigue High blood pressure Increased serum creatinine Swelling

CTCAE Management/

Symptoms^a

Differential

Event(s)	v4.03 Grade		Action/Supportive Care Guidelines	Diagnosis
Skin events 
 • Dermatitis • exfoliative Erythema • multiforme Stevens-Johnson syndrome Toxic epidermal necrolysis 	Grade 1-2	No change in dose	Symptomatic treatment should be given such as topical glucocorticosteroids (eg, betamethasone 0.1% cream or hydrocortisone 1%) or urea-containing creams in combination with oral antipruritics (eg, diphenhydramine HCl or hydroxyzine HCl). Treatment with oral steroids is at investigator discretion for Grade 2 events.	All attempts should be made to rule out other causes such as metastatic disease, infection, or allergic dermatitis.
	Grade 3	Hold IMMUNOTHERAPY.	Consider dermatology consultation and biopsy for confirmation of diagnosis. 
 • Treatment with oral steroids is recommended, starting with 1 mg/kg prednisone or equivalent once per day or dexamethasone 4 mg four times orally daily. When symptoms improve to Grade 1 or less, steroid taper should be started and continued over no less than 4 weeks. 	
	Grade 4	Permanently discontinue IMMUNOTHERAPY.	Dermatology consultation and consideration of biopsy and clinical dermatology photograph. Initiate steroids at 1-2 mg/kg prednisone or equivalent. When symptoms improve to grade 1 or less, steroid taper should be started and continued over no less than 4 weeks.	
If considered to be immune related, ≥ Grade 3 or result in dose modification or discontinuation: 
 • Pruritus • Rash • Rash generalized • Rash maculo-papular • Vitiligo 	≤ Grade 1	No change in dose		
	Grade 2	No change in dose		
	Grade 3	No change in dose	Grade 3 drug-related thrombocytopenia >7 days or associated with bleeding requires discontinuation.	
	Grade 4	Hold IMMUNOTHERAPY until resolves to ≤ Grade 1. May increase the dosing interval by 1 week.	Grade 4 drug-related thrombocytopenia >7 days or associated with bleeding requires discontinuation.	
Thrombocytopenia				

^a The signs and symptoms may be associated with any of the diagnoses in the associated "Event(s)" column.

^b REMICADE (Infliximab) prescribing information

^c If symptoms indicate possible new or worsening cardiac abnormalities, additional testing and/or a cardiology consultation should be considered.

